restricted based on race or ethnicity. Efforts will be made to recruit at least 15% minorities. Since COPCs are identified more often among women than men, we will actively recruit at least 25% males. All participants will get assistance in downloading both the pain app and Quell Relief mobile app and have access to a research assistant (RA) who will answer any questions and help manage any problems that the individual may encounter. All participants will also be given a more extensive battery of QST testing at baseline and again at the end of the study. We will use an enriched design by first having the potential subjects try the Quell device. We anticipate that very few potential study participants will decide not to participate in a trial because they dislike the feeling of the Quell based on the results of previous trials. If they find that they would be willing to use the device they will be included in the study. If they dislike using the device on an initial trial, their age, gender, ethnicity and pain duration will be noted and the participants will be thanked for their interest in the study and dismissed.

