All subjects (Quell and Sham Quell condition) will be encouraged to use their assigned device for at least 3 therapy sessions (3 hours of stimulation) every day, and to wear the device as often as possible, including while sleeping. Tracking of use of the device will be available electronically through the Quell Relief mobile app (subject data will be de-identified on the Quell server). All demographic and daily pain assessment data will be stored on a secure server (Mass General Brigham Amazon Web Server - MGB AWS) using the Veracode-tested study pain app and portal. Messages will be sent via the 2-way messaging pain app program to help track use of the device and to monitor and encourage active participation. Subjects will be instructed to enter daily assessments only when they are wearing the Quell device. Patients who wish to discontinue the study will be allowed to do so at their request. If the participant is willing, we will meet with her or him to understand reasons for discontinuing the study and problem-solve to see if there would be a way to keep following the individual. All subjects will be asked to complete a packet of questionnaires at the conclusion of the first 6-week study phase and then at the 3-month mark. All subjects will also be asked to participate in the full QST session described below at baseline, and then again at the end of the study (i.e., QST will be completed at the same poststudy visit when outcome measures are collected). Each subject will be compensated \$50 at baseline, \$25 mid study, and \$100 at study completion upon receipt of their completed questionnaires for a possible total of \$175. At the end of the study subjects will be informed which device was the standard Quell device and they will be encouraged to keep this device for future use. Those in the Sham treatment arm will be offered a standard Quell for use after the study. It is expected that 15% of the subjects will dropout before completing the trial and recruitment of a total of 115 subjects may likely be needed to successfully complete the study.

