Patient Measures: Participants will complete measures recommended by the Initiative on Methods, Measures, and Pain Assessment in Clinical Trials (IMMPACT; Dworkin et al, 2005; Gewandter et al., 2021) as primary outcomes. We will be tracking the patients using validated measures of pain (The Brief Pain Inventory - BPI), coping (Pain Catastrophizing Scale - PCS), level of disability (Pain Disability Index -PDI), mood (Hospital Anxiety and Depression Scale - HADS), presence of neuropathic pain (Pain Detect Neuropathic Pain Questionnaire - painDETECT), pain symptoms and function (Symptom Impact Questionnaire - SIQR), impression of change (Patients' Global Impression of Change - PGIC), healthcare utilization (monthly clinic and ED visits), and overall satisfaction (Satisfaction and qualitative questions developed for this study specifically related to use of a pain management device; see Table 1). We will also track daily ratings of pain, sleep, activity interference, and mood through the pain app. Objective measures of activity, gait, and sleep will be collected by the devices. The 7-item activity interference scale of the Brief Pain Inventory will serve as the primary outcome.

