Research Objectives: This study is expected to take 18-24 months to complete and is designed to gather information about the use of the Quell for persons with COPCs. We hypothesize that those using the Active Quell device will report reduced pain compared with the Sham Quell condition. We also expect that those using the active device will show improvement in sleep, mood, and level of activity over the 3-months of using the device. We hypothesize that frequency of using the Quell (increased tolerability and adherence) will be correlated with greater reduction in pain. We hypothesize that the device will be safe to use and will demonstrate a reduction in healthcare utilization (reduced clinic and ED visits). We will also investigate use of prescription opioids and other nonopioid pain medications among the study subjects and determine the effect of daily use of the Active Quell (vs. Sham Quell) on intake of prescription pain medication. Finally, based on preliminary analyses from prior Quell studies, we will investigate whether certain individuals report greater benefit from using the Active Quell than others and, in particular, we predict that those with more pain sensitivity and longer duration of pain will demonstrate most benefit from the Active Quell. The previous studies in LBP and fibromyalgia patients both yielded evidence that the most pain-sensitive patients reported the greatest reductions in pain with Active Quell use. In the present proposal, we will be recruiting participants with evidence of sensitization at baseline and we will evaluate whether the most-sensitized patients with COPCs, even within a generally sensitized group of patients, show the greatest analgesic benefits. We will examine trends from the daily pain ratings on the pain app since it gives multiple daily pain ratings over the course of the study. We will target the 7-item activity interference subscale of the BPI (0=does not interfere; 10=completely interferes) as the primary outcome, and the PCS, PDI, HADS, painDETECT, SIQR, PGIC, healthcare utilization, and satisfaction questions as secondary outcome measures.

Statistical POW

Power calculations, as outlined by Cohen (1988), were performed to determine the probability of detecting clinically significant differences between treatment conditions in the primary area of measurement. These calculations assumed a two-tailed test and alpha level of 0.05 confirming the

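### The plan hypothesises that the device is safe, but its visible text names no adverse-effect outcome, systematic collection or between-arm safety analysis

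*Combined protocol and SAP*

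**What the plan says.** Research Objectives states the safety hypothesis: "We hypothesize that the device will be safe to use". The full sentence joins it to service use: "We hypothesize that the device will be safe to use and will demonstrate a reduction in healthcare utilization (reduced clinic and ED visits"). No endpoint, threshold or analysis for safety follows. After the primary outcome (BPI activity interference), the same section lists "and the PCS, PDI, HADS, painDETECT, SIQR, PGIC, healthcare utilization, and satisfaction questions as secondary outcome measures".

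Patient Measures describes the service-use measure as "healthcare utilization (monthly clinic and ED visits"), with no mention of the cause of a visit. It also lists satisfaction and qualitative questions about using a pain device and refers to Table 1, whose items do not appear in the public text.

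Research Design and Methods touches on tolerability in three places:

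- **Try-out before entry.** "We will use an enriched design by first having the potential subjects try the Quell device". The sponsor expects few refusals: "We anticipate that very few potential study participants will decide not to participate in a trial because they dislike the feeling of the Quell". For those who do refuse, "If they dislike using the device on an initial trial, their age, gender, ethnicity and pain duration will be noted", and they are then dismissed.
- **Discontinuation.** "If the participant is willing, we will meet with her or him to understand reasons for discontinuing the study".
- **Support.** Every participant can contact a research assistant about problems, and a 2-way messaging function is in use. No rule says how reported problems are recorded.

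The analysis text that follows the power calculation deals with change scores, the daily pain ratings and imputation of the efficacy measures. It contains no safety analysis.

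**The concern.** A hypothesis that is to be reported needs a measure that could contradict it. Here the harms one would expect to ask about with a worn stimulator, such as skin reactions and discomfort from stimulation, are not tied to any visible question put to all subjects at the same times.

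The question is relevant to this design. Subjects are selected for sensory hypersensitivity, are encouraged to complete at least 3 hours of stimulation a day for 12 weeks, and are asked to wear the device as much as they can, including in sleep. The sham differs only in the amount of stimulation, so a common question in both arms would give a direct view of what the longer stimulation adds. Without that question, the trial could report scattered complaints but no rate and no Active-Sham difference.

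**Working it through.** The plan states no safety figure, so there is none to reproduce. The main check is to set each source that could carry safety information against what the hypothesis needs.

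| Source (section) | Who supplies it | What it can show | What it leaves open |
|---|---|---|---|
| Clinic and ED visits (Patient Measures) | All, both arms | A rise or fall in visits | Cause of visit; problems that lead to no visit |
| BPI, SIQR, PGIC (Patient Measures) | All, both arms | Worsened pain or overall state | Skin reactions, local discomfort |
| Satisfaction and qualitative questions (Patient Measures, Table 1) | All, both arms | Possibly side effects | Items not visible; not named as a safety outcome |
| Daily app ratings (Patient Measures; Research Design and Methods) | All, but only while wearing the device | Pain, sleep, activity interference, mood | Days on which the device is off because of a problem |
| Device-use tracking (Research Design and Methods) | All, both arms | Falling use | Why use fell |
| Talk at discontinuation (Research Design and Methods) | Willing discontinuers | Reasons for stopping | Everyone else |
| Try-out (Research Design and Methods) | Candidates before entry | That someone disliked the device | The specific complaint |

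No row gives a named adverse-effect outcome with common timing and an analysis by arm. The third row might supply the question, but the visible text does not supply the outcome or the analysis.

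**What the sample could show if events were collected.** Inputs: 50 completers per arm; 115 recruited at 1:1, so 115/2 = 57.5, taken as 57 per arm. With 0 events in n subjects, the exact upper limit is 1 − α^(1/n), with α = 0.05 for a one-sided 95% limit and α = 0.025 for the upper end of a two-sided 95% interval.

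- n = 50: 1 − 0.05^(1/50) = 5.8%; 1 − 0.025^(1/50) = 7.1%.
- n = 57: 1 − 0.05^(1/57) = 5.1%; 1 − 0.025^(1/57) = 6.3%.

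The chance of seeing at least one event in 50 is 1 − (1 − p)^50. For assumed true rates p of 1%, 2% and 5%, it is 39%, 64% and 92%. These rates are illustrations and do not come from the documents.

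**What a comparison of arms could show.** With 50 per arm and a two-sided 5% test, power is about 38% for assumed rates of 5% against 15%, 62% for 5% against 20%, and 81% for 5% against 25%. A safety comparison would therefore be descriptive.

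These figures describe the sample size. They do not measure the gap in the plan and would be the same after the fix. Their use is to show how a safety conclusion should be worded.

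**The case against.** The strongest reply is that the plan does collect information bearing on safety from everyone. Visits, PGIC, the pain and function scales and the device-use questions are obtained in the same way in both blinded arms. Worsened pain, one obvious harm, is thus captured. The sentence stating the safety hypothesis also mentions clinic and ED visits, which can show an increase as well as a reduction. Table 1 may hold a side-effect item.

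Much of this stands, and it rules out several stronger readings that a reader might infer:

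- **That nothing related to safety is measured, or that the discontinuation talk is the only inquiry.** The measures just listed contradict this, and with Table 1 not visible a side-effect item cannot be excluded.
- **That the try-out makes the arms non-comparable.** It comes before entry and applies to both arms alike. It limits generalizability and may understate intolerance, and the sponsor expects few refusals. The broad reason for refusing (dislike) is known; only the specific complaint is missing.
- **That safety would be accepted by default.** The plan gives no acceptance rule, so this would be speculation.

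What the reply does not supply is a named safety outcome or an analysis. Visit counts without a cause do not identify device effects, and skin irritation or discomfort need not lead to a visit. Even if Table 1 contains a suitable item, the outcome list and the analysis text do not designate it for the safety hypothesis.

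**Conclusion.** The point holds in a limited form. Safety is hypothesised, and the visible text specifies no adverse-effect outcome, no systematic collection and no between-arm safety analysis. The indirect measures cover worsened pain and service use in both arms, but skin reactions and stimulation discomfort have no assured common capture. Followed as written, the plan could not answer the safety hypothesis as an Active-Sham comparison.

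The conclusion rests on the visible text. If Table 1 has an adverse-effect item, the gap narrows to naming and analysing it. No numerical size can be put on the omission itself. The primary efficacy inference does not depend on it. The change is worth making because it is cheap and alters what the trial can conclude.

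**What to change.** - **Collect.** Add one fixed adverse-effect item to the existing 6-week and 3-month packets, identical in both arms: type (skin irritation, discomfort from stimulation, worsened pain, other), severity, and whether use was stopped. If Table 1 already has such an item, name it as the safety outcome. Take spontaneous reports through the existing 2-way messaging, with a simple log, so that no new app function is needed. Put the same item to discontinuing subjects who agree to talk, since someone who leaves before week 6 would otherwise miss it.
- **Analyse.** Define the outcome as subjects with any device-related adverse effect. Report the proportion in each arm and the difference, with 95% confidence intervals, as a descriptive comparison. Keep the rate in each arm in view as well as the difference: both arms wear the device, so effects of wearing it would largely cancel in the difference.
- **Try-out.** Record the specific reason when a candidate declines, and report these reasons next to the in-trial rates.
- **Conclude.** Restate the hypothesis as an estimate with its upper confidence limit, for example 0 of 50 with an upper limit of 5.8% one-sided or 7.1% two-sided, in place of an unqualified claim of safety.

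The cost is one questionnaire item, one extra column in the try-out record and a log of messages, with no added visits. The downside is slightly longer packets and a more modest safety statement.

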Patients will be excluded from participation if they meet any of the following criteria: (1) diagnosis of cancer or any other malignant disease, (2) acute osteomyelitis or acute bone disease, (3) present or past DSM-V diagnosis of schizophrenia, delusional disorder, psychotic disorder, or dissociative disorder that would be judged to interfere with study participation, (4) pregnancy, (5) any clinically unstable systemic illness judged to interfere with treatment, (6) a pain condition requiring urgent surgery, (7) an active substance use disorder, such as cocaine or IV heroin use (positive on the Mini International Neuropsychiatric Interview; M.I.N.I. v.5.0), that would interfere with study participation, and (8) have an implanted cardiac pacemaker, defibrillator, or other implanted device. All subjects will be asked to not change their treatment during the study period, (9) Raynaud's syndrome, or (10) Open cuts/sores.

Patients will be equally randomized to one of two experimental groups in this trial (i.e., Active Quell or Sham Quell) with the goal of having 50 subjects complete the trial in each group. The Sham Quell will look exactly like the Active Quell but will be programmed to give 2 minutes of stimulation three times during the 1-hour therapy session (2 minutes of stimulation at 0, 28, and 58 minutes, etc.). Subjects will be told that they will be exposed to two treatment conditions, lower intensity or higher intensity stimulation, and will be asked to use the device (standard or sham) every day for 12 weeks. Neither the investigators nor the study participants will know for sure which device they will be receiving. All subjects will complete assessment measures and be followed for 3 months. Recruitment will not be

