hypotheses that the Active Quell would be associated with general overall improvement in activity interference on the activity subscale of the Brief Pain Inventory. In our previous work (Jamison, Wan et al., 2019; Jamison, Curran et al., 2021; Jamison, Edwards et al., 2021), we had a high rate of consent to participate among recruited patients, with minimal attrition. We assessed power based on our preliminary data and previously published studies. The power analysis revealed that a sample size of 100 subjects (50 per treatment arm) using a 2-sample t-test for a difference in mean pre/post change score gives the study a >85% probability of detecting a 1.5-point group difference on a 0-10 rating scale (assuming a standard deviation of 1.8). Conventional metrics suggest that a 30% change or difference score is clinically meaningful (Dworkin et al., 2021), and this sample size would provide adequate power to detect a group difference of approximately 20%. Most of the analyses in the proposed study will involve delta scores reflecting changes within subjects (both uncorrected and adjusted - least squares, LS). We also will conduct multi-level modeling analyses of the daily pain assessments. We will examine the distribution of the delta scores between treatment arms and will ascertain whether that distribution is normal. This information will allow us to determine whether parametric (e.g., ANCOVA) or nonparametric analyses should be used. Collectively, this sample size (n=100 total), together with our previously observed very high retention rates and the substantial efficacy of the device, will provide more than adequate power to detect moderate-size effects.

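### Does asking subjects not to change treatment make the Active versus Sham comparison of pain medication intake uninterpretable?

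*Combined protocol and SAP*

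**What the plan says.** Research Design and Methods, within the list of exclusion criteria, states: "All subjects will be asked to not change their treatment during the study period". The sentence applies to both arms. Treatment is not defined there or elsewhere in the available text, and pain medication is neither named nor exempted.

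Research Objectives adds: "We will also investigate use of prescription opioids and other nonopioid pain medications among the study subjects". The same sentence then sets the comparative aim, to "determine the effect of daily use of the Active Quell (vs. Sham Quell) on intake of prescription pain medication".

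Intake has no further status in the plan. The BPI activity interference scale is the primary outcome, and the same section names "PCS, PDI, HADS, painDETECT, SIQR, PGIC, healthcare utilization, and satisfaction questions as secondary outcome measures". Patient Measures says of the app: "We will also track daily ratings of pain, sleep, activity interference, and mood through the pain app". Medication is not in either list. Patient Measures also cites a Table 1 that is not in the available text, so it cannot be said that intake goes unmeasured.

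The power section rests on "a sample size of 100 subjects (50 per treatment arm) using a 2-sample t-test for a difference in mean pre/post change score" and concerns BPI interference only. It gives no power, test or interpretation rule for intake.

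**The concern.** Read side by side, the two statements seem to pull against each other. One asks subjects to hold treatment constant, and the other treats a component of treatment as something the device might alter. In a chronic pain population a subject could reasonably take treatment to include prescription pain medication. To the extent that subjects do so and comply, change in intake moves toward zero in both arms and the difference between arms shrinks.

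At stake is the reading of a null. A report could say that the device does not affect medication intake when the result partly reflects a request to keep intake stable. The aim is also worded as determining an effect, which sounds confirmatory for a quantity with no stated outcome status or analysis.

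**Working it through.** **1. The two possible readings.**

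| Reading of treatment | Consequence for intake |
|---|---|
| Pain medication, or at least as-needed use, not covered | Intake is free to vary and the statements are compatible. Only the usual caution about a non-significant result applies. |
| Pain medication covered | Intake may be held near baseline in both arms. The comparison estimates the effect of assignment under the request. |

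Under the second reading, allocation is still 1:1 (Blinding section) and the request is the same in both arms, so neither arm is favoured. A difference is a valid effect of assignment under the request. A null is, by the same logic, a valid though imprecise estimate of that same effect. What it does not support is a statement about intake when subjects are free to change it.

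**2. The plan's own power figure.** Inputs from the power section are 50 per arm, a difference of 1.5, an SD of 1.8 and two-sided alpha 0.05. The standardized difference is 1.5/1.8 = 0.833, and the two-sample t-test then has 98.5% power. The stated value of more than 85% holds as a lower bound. It concerns BPI interference and says nothing about intake.

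**3. Precision for intake, in SD units.** No SD or test for intake is given, so the t-test is borrowed from the BPI calculation as an assumption. The 95% half-width is t(0.975, 2n−2) × √(2/n).

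| n per arm | Source | t | √(2/n) | Half-width (SD) | Difference detectable with 80% power (SD) |
|---|---|---|---|---|---|
| 50 | power section | 1.984 | 0.200 | 0.397 | 0.566 |
| 40 | assumed | 1.991 | 0.224 | 0.445 | 0.634 |
| 25 | assumed | 2.011 | 0.283 | 0.569 | 0.809 |

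The lower two rows cover the case where only some subjects take prescription pain medication, since the documents do not give that number. The request enters none of these formulas. The table describes any continuous outcome at these sizes and does not measure the concern.

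**4. Attenuation, as an illustration only.** Suppose a true effect of d = 0.5 SD on freely varying intake, and a share f of subjects in each arm who hold medication fixed. Both values are assumed.

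- With nobody holding medication fixed, power at 50 per arm is 70%.
- Multiplying the standardized effect by (1 − f) and leaving the SD at 1 gives, for f = 0.5, an effect of 0.25 and power of 24%.
- That overstates the loss, because subjects with zero change also reduce the variance. With SD 1 among the others, the average variance over the two arms is (1 − f)(1 + f·d²/2) = 0.5 × (1 + 0.5 × 0.25/2) = 0.531, so the SD is 0.729. The standardized effect is 0.25/0.729 = 0.343, and power is about 40%.

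Power does fall, but by how much depends entirely on f and d, and the documents give neither.

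**The case for a change.** The strongest case for a change is that a stated between-arm aim should be interpretable whichever way it comes out. One clarifying sentence in the design section and one or two in the objectives would cost nothing in data or sample size. Settling the reading before unblinding would also stop it from being chosen after the results are known. Nothing in the available text defines treatment, exempts as-needed use or guards against misreading a null.

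The factual part stands. The word is undefined, and if medication is covered the difference may be attenuated. The claim that a null could not be read as absence of a device effect is too strong, because it depends on one of the two readings. The feared conclusion is also a predicted misreport, since no passage says a null will be taken as no effect. Labelling intake exploratory would add little, because it is already outside the named primary and secondary outcomes and has no power claim. The clarification would change no data, estimate, test or stated figure. Finally, consent pages are not part of the available documents, so what subjects are told in detail cannot be judged from here.

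**Conclusion.** This is a gap in wording that analysts can fill sensibly, and it calls for no change to the plan. The request and the intake objective conflict only if treatment is taken to include pain medication. Even then, the comparison by randomized arm is valid for the effect of assignment under a common request. A null would be imprecise (half-width about 0.40 SD at 50 per arm, wider if fewer subjects take prescription pain medication) and would not generalize to unrestricted use. A competent report would present the estimate by arm with its 95% confidence interval, treat it as exploratory because it is not a listed outcome, and state the request as context.

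No size can be put on the attenuation from the documents, and the 40% power figure above rests on assumed inputs. The primary BPI interference comparison does not depend on how the word is read. Whether the request covers pain medication is for the sponsor to say, and this review takes no view on it.

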Multivariate imputation with chained equations (MICE) will be used to fill in missing assessments (including for subjects that drop out). MICE is valid under the assumption that data is missing at random (MAR). Variables will be modeled using normal regression. For each efficacy measure, the imputation model will include the available baseline, week-6 and 3-month data, demographics (age, BMI, education) and pain characteristics. The active and sham groups will be separately imputed. The same random-number seed will be used for computation of 250 complete (i.e., no missing data) datasets for each efficacy measure. For each dataset, the 3-month least-square mean change scores will be determined. The results will then be combined according to Rubin's rule. A sensitivity analysis for data missing not at random (MNAR) rather than MAR will be performed using delta-based MI. Specifically, the LS mean change scores will be reanalyzed with deterministic increases to the 3-month assessments (i.e., smaller change scores) of subjects on active treatment that withdrew from the study.

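### Do the undefined terms in the power section's closing claims call for a change to the plan?

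*Combined protocol and SAP*

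**What the plan says.** The power section rests on one calculation. At its start it fixes the error rate: "These calculations assumed a two-tailed test and alpha level of 0.05". It then takes 100 patients, 50 per arm, "using a 2-sample t-test for a difference in mean pre/post change score", and reports that this "gives the study a >85% probability of detecting a 1.5-point group difference on a 0-10 rating scale (assuming a standard deviation of 1.8").

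Two broader statements follow. After citing 30 per cent as a clinically meaningful change or difference, the section says that "this sample size would provide adequate power to detect a group difference of approximately 20" per cent. It ends by saying that the sample size, together with high retention and the efficacy of the device, "will provide more than adequate power to detect moderate-size effects".

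The same section says that most analyses will use within-patient change scores, "both uncorrected and adjusted - least squares, LS", and names ANCOVA as the parametric option once the distribution has been examined. The missing-data paragraph at the end of the document says that multiple imputation "will be used to fill in missing assessments (including for subjects that drop out"), and adds: "For each dataset, the 3-month least-square mean change scores will be determined".

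The primary outcome is the seven-item Brief Pain Inventory interference subscale, scored 0 to 10. The document gives no expected baseline mean for it. The entry threshold of 4 in the Research Design and Methods section applies to pain intensity, not interference.

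**The concern.** The computed scenario is a difference of 0.83 SD. Good power there says nothing about smaller effects, yet both broader statements concern smaller effects, or effects of unstated size, and neither has a calculation behind it.

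If moderate is taken as 0.5 SD, the planning t-test has about 70% power, which few would call more than adequate. If 20 per cent means 20 per cent of a baseline interference score of 4, power is about 60%. A reader facing a null primary result might rely on these sentences and conclude that a difference of about 0.9 points had been ruled out, when the planning test would miss it roughly three times in ten.

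**Working it through.** **Inputs.** From the power section: two-sided alpha 0.05, n = 50 per arm, SD of change 1.8, two-sample t-test. Assumed here, because the document gives no value: the standardised size of a moderate effect, the base for 20 per cent, and the pre/post correlation r.

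**Formula.** With d = difference / 1.8, power is the noncentral-t probability with 98 degrees of freedom and noncentrality d × √(n/2) = 5d. The normal approximation is Φ(5d − 1.960).

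**1. The plan's own figure.** d = 1.5 / 1.8 = 0.833 and the noncentrality is 4.167. The normal approximation gives Φ(2.207) = 98.6%; the noncentral t gives 98.5%. The stated lower bound of 85% holds.

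**2. Detectable difference.** By the normal approximation, 80% power needs (1.960 + 0.842) × 1.8 × √(2/50) = 1.01 points. The exact t calculation gives 1.02 points (d = 0.57), and 1.18 points (d = 0.65) for 90%.

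**3. Moderate effects, unadjusted t-test.**

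| Assumed d | Points | Power |
|---|---|---|
| 0.4 | 0.72 | 51% |
| 0.5 | 0.90 | 70% |
| 0.6 | 1.08 | 84% |

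The answer falls on either side of 80% depending on the definition chosen.

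**4. Percentage effects, unadjusted t-test, by assumed base.**

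| Base | 20% of base | Power | 30% of base | Power |
|---|---|---|---|---|
| 4 | 0.8 | 60% | 1.2 | 91% |
| 5 | 1.0 | 79% | 1.5 | 98.5% |
| 6 | 1.2 | 91% | 1.8 | 99.9% |

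At a base of 7, 20 per cent is 1.4 points, with 97% power. As 20 per cent of the 0 to 10 range it is 2.0 points, with power above 99%. The base needed for 80% power is 1.0186 / 0.20 = 5.09 for the 20 per cent difference and 1.0186 / 0.30 = 3.40 for the 30 per cent benchmark.

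**5. Baseline adjustment.** Assume that baseline is the covariate and that pre and post variances are equal. The residual variance is then the change-score variance × (1 + r)/2. At d = 0.5:

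| Assumed r | 50 per arm | All 115 fully informative (upper bound) |
|---|---|---|
| 0.3 | 87% | 91% |
| 0.5 | 82% | 87% |
| 0.6 | 79% | 84% |
| 0.7 | 77% | 82% |

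With 50 per arm, 80% is reached when 0.566 × √((1 + r)/2) ≤ 0.5, that is, for r up to about 0.56. For r from 0.7 down to 0.3 and 50 per arm, 20 per cent of a base of 5 has 85% to 93% power, and 20 per cent of a base of 4 has 67% to 78%. At d = 0.4 power stays below 80% throughout: 58% to 69% with 50 per arm, and 64% to 75% with all 115.

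**The case for a change.** The best case for a change is as follows. The closing sentence is tied to 100 patients, so recruiting 115 does not support it. The two supports it names add nothing: retention is already used in assuming 100 completers, and the efficacy of the device is what the trial tests, so it cannot raise power at a fixed effect size. Adjustment is no firm rescue either, because ANCOVA is only the option if the data look normal and neither covariate nor correlation is stated. The 1.5-point target can be read as the 30 per cent benchmark (base 5, so 20 per cent is 1.0 point, 79% power) or as the 20 per cent difference itself (base 7.5, 98.5% power). Two sentences of text would settle all this at almost no cost.

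Most of these observations are correct, and the planning test alone does not establish either broad statement. They do not show that either statement is false. The document gives no standardised effect and no baseline interference score, so each failing case uses a value brought from outside. The section says power was based on preliminary data and published studies, which may well supply the base.

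Nor is the reader of a null result left without an answer. Alpha, sidedness, test, sample size and SD are all stated, and the detectable difference of about 1.0 point follows from them directly. Once the trial has run, the confidence interval for the difference will show which effects are excluded, whatever the planning text said.

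**Conclusion.** No change is needed. The single computed figure is correct and conservative: about 98% against a stated bound of 85%. What remains is loose wording in two summary sentences, not an arithmetic error.

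On the planning t-test, the 20 per cent claim holds for a base of about 5.1 points or more. The moderate-effect claim reaches 80% power only if moderate means at least 0.57 SD. With baseline adjustment, power at 0.5 SD is 77% to 87%, given an SD of change of 1.8, equal pre and post variances and r between 0.7 and 0.3. An effect of 0.4 SD stays underpowered on any of these readings, but the plan does not say that moderate means 0.4.

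The comparison that matters most to the plan's own argument is the 30 per cent benchmark, and it is well powered for any base above about 3.4 points. Defining the two terms would be a courtesy to readers; it would alter no sample size, endpoint, analysis or decision.
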